The Data Monitoring Committee (DMC) will review the progress of the study and will monitor subject intake, outcomes, serious adverse events, and other issues related to subject safety. The DMC makes recommendations to the Director of the Clinical Science Research and Development (CSRD) Service about whether the study should continue or be stopped. The DMC will consist of experts in the fields of Endoscopic Vein Harvesting, Cardiothoracic Surgery, Cardiology, clinical trials, biostatistics, and ethics. These experts will not be participants in the trial and will not have participated in the planning of the protocol. The DMC will consider safety or other circumstances as grounds for early termination, including either compelling internal or external evidence of treatment differences or the unfeasibility of addressing the study hypothesis (e.g., poor subject enrollment, poor adherence to protocol).

At each of its meetings during the study period, the DMC will review the randomization rates and assess the difference between the actual and the projected rates, as well as the impact of these assessments on overall trial size. An assessment of whether the trial should be continued will be made followed by recommendations, as appropriate. All serious adverse events will be reported on a regular basis to the DMC for their review. Unexpected serious adverse events may be reported to the DMC in an expedited manner based upon the consensus of the Study Chairman, the Study Biostatistician, and the Perry Point CSPCC Director. The Study Biostatistician will provide the appropriate data to the DMC at specified intervals for this purpose.

The Clinical Events Committee (CEC) will consist of one cardiologist and two cardiac surgeons who will meet semi-annually (either in person or via conference calls). This committee will systematically evaluate all study deaths for cardiac versus non-cardiac causes. The national nurse coordinator will prepare a Clinical Events packet for each subject death which will consist of notes, labs, tests from the subject's medical record and death certificates or autopsy reports when available. In addition, this committee will evaluate and confirm all reported myocardial infarctions (MI) using the published AHA/ACC/ECS Universal criteria (Thygesen 2007). This may be accomplished using notes, labs and diagnostic tests from the subject's medical record. To assure compliance with data security

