procedures, all necessary documentation will be “scrubbed” to remove subject identifiers and any reference to treatment arm received.

The local sites IRB will be the study’s primary IRB and the IRB of record for the study. It will be responsible for the initial and continuing IRB reviews of the study. The local site IRB must review and approve amendments (changes to inclusion/exclusion criteria, protocols, informed consents, etc.), deviations, and review reports about serious adverse events and problems, complaints, terminations, etc. and that the investigators must provide the local site IRB all supporting documentation. The CSPCC will be responsible for providing the local site IRB with all materials that are required for each review and to respond to local IRB’s queries and requests for additional materials. The local site IRB approves the original informed consent template and any requested changes to the informed consent forms.

The Human Rights Committee (HRC) at the Coordinating Center will review the study prior to its initiation to the local site IRB to ensure proper protection of the subjects’ rights and safety. The CSPCC HRC will also conduct at least one site visit during the study to interview study subjects to assess whether subject rights are being fully protected.

CSP SMART will provide GCP training at the kick-off meeting and will conduct initiation visits at all sites. It also will conduct a GCP site review and a for cause audit of a participating site if requested by any of the monitoring bodies. At a minimum, each site will be visited at least once during the study by SMART. The local site IRB will receive a copy of all SMART monitoring reports.

The Quality Assurance Section at the Perry Point CSPCC will provide central monitoring of study sites to ensure compliance with Good Clinical Practice. Monitoring may include but is not limited to the informed consent process, data validation, source verification, and safety reporting. Additional site-specific monitoring may be conducted if triggered by poor study performance. Site performance findings may result in on-site visits by the CSPCC QA Nurse Specialist or other CSPCC central monitoring personnel to evaluate the need for additional site training to remedy compliance concerns.

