16 SITES

Justification for Patient Payments:

No payment for enrollment in this study will be provided. However, a small payment (\$50.00) will be provided to all participants returning for their six week clinic visit. This payment is provided to assist the participant for time and travel expenses.

VA COOPERATIVE STUDY #588

RANDOMIZED ENDO-VEIN GRAFT PROSPECTIVE – REGROUP TRIAL

Guidance for the Definition of Type 5 Myocardial Infarction (MI related to CABG)

- The CSP#588 Executive Committee has recognized the need to clarify a working definition to be used in the REGROUP Trial for Myocardial Infarction (MI).
- The updated Third Universal Definition of MI published in 2012 was cited as a reference for the Executive Committee discussion [Thygesen 2012].
- The purpose of this clarification for the definition of MI is to capture every and all MI events during the conduct of the study while minimizing the volume of site reports that do not meet the definition of MI.
- As a modification to the currently approved protocol, no cardiac biomarkers (including troponin) will be routinely required as a study procedure at any time point (including baseline or postop). The case report forms will have indicators for these tests and corresponding reference ranges to be captured only if performed for clinical purposes and are available in the medical record of a consented subject for CSP#588.
- Electrocardiograms (12 lead ECG) will continue to be required on post-op day#1 and #2 as stated in the currently approved protocol, however these are performed for clinical purposes at every site at these same time points (POD#1 and POD#2) regardless of the study protocol.
- ECG abnormalities that indicate the need for cardiac biomarker workup include new pathologic Q waves or new left bundle branch block.
- In the event an ECG abnormality as described above, or clinical suspicion, causes concern for MI, cardiac biomarkers will be obtained. This is standard clinical practice. Cardiac Troponin I (cTn I) , cardiac Troponin T (cTn T) or CPK-MB will be obtained every 8 hours until a downward trend is seen in the level. The preferred cardiac biomarker is cTn I.
- The troponin will be considered indicative of MI if the peak level > 10 x 99th percentile of the upper reference limit (URL) **in the first 48 hours after CABG**. The existing principles [Thygesen Circulation 2012] for the universal definition of MI should be applied for the definition of MI > 48 hours after surgery.

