- The cardiac biomarker level does not stand alone in the diagnosis of MI for post-op CABG patients, it must be accompanied in the same setting with **at least one of the following:**
 - 12 lead ECG with new pathologic Q waves or new left bundle branch block, or
 - angiographic documented new graft or new native coronary artery occlusion, or
 - imaging evidence of new loss of viable myocardium or new regional wall motion abnormalities.

- In the event cardiac biomarker work-up and ECG interpretations do not provide a complete diagnostic profile to the satisfaction of the surgeon investigator, a transthoracic echocardiogram would be the next clinical step to ascertain if a true MI occurred as evidenced by a new regional wall motion abnormality, with the exception of the septal wall.
- For the purposes of this study, septal wall motion abnormalities (which are prevalent in the postoperative phase) are excluded from the Definition of MI.

Introduction:

CSP #588 - REGROUP is a randomized, intent-to-treat, two-arm, parallel design, multicenter study. Cardiac Surgery Programs at Veterans Affairs Medical Centers (VAMC) with expertise in performing both EVH and OVH will be invited to participate in the study. Subjects requiring elective or urgent CABG using cardiopulmonary bypass with use of at least one SVG will be screened for enrollment using established inclusion/exclusion criteria. Enrolled subjects will be randomized to one of the two arms (EVH or OVH) after an experienced vein harvester is identified and assigned. Assessments will be collected at multiple time points including: intraoperatively, postoperatively, at discharge or 30 days after surgery if still hospitalized. Assessment of leg wound complications will be completed at the time of discharge and at six-week post-surgery. Telephone follow-ups will occur at three-month intervals post-surgery until the participating sites are decommissioned at the end of the trial period (which would be approximately 4.5 years after the site initiations). For long-term MACE outcomes, passive follow up for MACE events using VA databases (CPRS, VASQIP) will be performed centrally by the Study Chair's office for another 2 years.

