Randomization and Data management will be performed by the VA CSPCC [name]. An Interactive Touchtone Telephone Randomization System (ITTRS) will be used to set up the randomization system. Clinical DataFax System, a data management software will be used for data management. The CSPCC will have overall responsibility for the data at the end of the study.

Randomization

After a patient at any of the participating centers is consented, successfully screened and has provided baseline information, s/he will be assigned to a harvester. Once a harvester is assigned and available for the harvesting of the required vein, the patient will be randomized. The research coordinator will place a call to the ITTRS (a dedicated 1-800 phone number will be provided) to randomize the patient in one of the two harvesting techniques – endoscopic and open vein harvesting techniques. Once the required information is entered in the system, the system will return the assignment for the patient. This study will use a “permuted block” randomization scheme where random block sizes of two and four will be used. The research coordinator will need the following information in order to complete a successful randomization call:

- a. Study number and study password (will be provided by CSPCC)
- b. 3-digit site number and password (will be provided by CSPCC)
- c. The subject's ID Number & ALPHA Code
- d. The subject's signed Informed Consent Form
- e. Form 01, Screening and Randomization
- f. Laminated Randomization Cheat Sheet

a. Data Capture during visits and/or telephone contacts

The system for data capturing will be designed by visits where a group of required CRFs will be assigned to each “visit” according to the “Schedule of Assessments” table.

FORM	SCREEN	BASELINE (pre op)	INTRA OP	POST OP	DC- 30 DAY	6 WK	3 MO	6 MO	9 MO	12 Mo	...	45 MO	49 MO	AS NEEDED
00-Screening Log	X													
01 – Screening and Randomization	X													
02 – Baseline Information		X												
03 – Seattle Angina Questionnaire		X				X				X				
04 – VR-12		X				X				X				
05 – Intraoperative Data Collection			X											
06 – Post Operative Assessments				X										
07 – Discharge Assessments					X									
08 – Leg Incision Pain Questionnaire					X									
09 – Leg Incision Pain 6 Week						X								
10 – Leg Incision Assessment					X	X								
11 – Mace Event (6 Week)						X								
12 – Phone Call Follow-up							X	X	X	X	X	X	X	
13 – MACE Event Form													X	
14 - Termination														X

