65. CASS SITE (DISTAL TARGET)					
1= Prox RCA	6= 1 st RPL	11= LMCA	16= 2 nd Diag	21= 2 nd OM	26= 3 rd LPL
2= Mid RCA	7= 2 nd RPL	12= Prox LAD	17= 1 st Septal	22= 3 rd OM	27= LPDA
3= Dist RCA	8= 3 rd RPL	13= Mid LAD	18= Prox Cx	23= Dist Cx	28= RAMUS
4= RPDA	9= Inferior Septal	14= Dist LAD	19= Mid Cx	24= 1 st LPL	29= 3 rd Diag
5= RPAV	10= Acute Marginal	15= 1 st Diag	20= 1 st OM	25= 2 nd LPL	30= Unknown

SITE NO.	SUBJECT ID	ALPHA CODE	DATE FORM COMPLETED																					

 	 	 	

				

 	 	 	 	

					

 	 	 	 	

					

 	 	

			

 	 	

			

 	 	 	 	

				
			Month	Day	Year																			

FORM 06 – POSTOPERATIVE ASSESSMENTS

1. POST-OP DAY #1.....

--	--

--	--

--	--	--	--

 month *day* *year*

2. ECG evidence of new pathologic Q waves or new LBBB: No Yes

If yes, obtain Cardiac Biomarkers of choice every 8 hours until downward trend is seen in level and
complete A, B, OR C below.

A. Peak Cardiac Troponin I

1. Peak Cardiac Troponin I (ng/mL):

--	--

 .

--	--
2. Reference Range (ng/mL)

--	--

 .

--	--

 to

--	--

 .

--	--

B. Peak Cardiac Troponin T

1. Peak Cardiac Troponin T (ng/mL):

--	--

 .

--	--
2. Reference Range (ng/mL)

--	--

 .

--	--

 to

--	--

 .

--	--

C. Peak CPK/MB Panel

1. Peak Total CPK (U/L):

--	--	--	--
2. Total CPK Reference Range (U/L)

--	--

 to

--	--	--	--

AND

3. Peak CK-MB (ng/mL):

--	--

 .

--	--
4. CK-MB Reference Range (ng/mL)

--	--

 to

--	--

 .

--	--

AND

5. Peak CK-MB Index (%):

--	--

 .

--	--
6. CK-MB Index Reference Range (%)

--	--

 .

--	--

 to

--	--

 .

--	--

3. ECG evidence of arrhythmia: No Yes

1. If yes, specify:
 - atrial fibrillation
 - atrial flutter
 - pacemaker
 - other, specify _____

4. Chest tube drainage (cc):

--	--	--	--

SITE NO.

--	--	--

SUBJECT ID

--	--	--	--

ALPHA CODE

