SITE NO. 

 	 	 	

				SUBJECT ID 

 	 	 	 	

					ALPHA CODE 

 	 	 	 	

					DATE OF VISIT 

 	 	

 Month			

 	 	

 Day			

 	 	 	 	

 Year				

FORM 11 – 6 WEEK MACE EVENT FORM

1. Has the subject died after the last contact? No Yes
(If yes, complete Forms 14 and 15)

a. Date of death

--	--

Month

--	--

Day

--	--	--	--

Year

2. Did the subject have an acute myocardial infarction since the last contact? No Yes
(If yes, complete form 15 and 19)

a. AMI Date

--	--

Month

--	--

Day

--	--	--	--

Year

3. Did the subject receive PCI since the last contact? No Yes
If yes,

a. Procedure Date

--	--

Month

--	--

Day

--	--	--	--

Year

4. Did the subject receive CABG since the last contact? No Yes
If yes,

a. Procedure Date

--	--

Month

--	--

Day

--	--	--	--

Year

For Q 1-4 answered yes, obtain appropriate medical records for required source documentation.

--	--	--

--	--	--	--

--	--	--	--

MEDICATIONS

5. Has the subject taken any of the following medications in since last contact?

a. Beta blocker	No 	Yes 
b. ACE/ARB Inhibitor	No 	Yes 
c. Statin	No 	Yes 
d. Non-Statin LLA	No 	Yes 
e. Nitrate	No 	Yes 
f. Calcium Channel Blocker	No 	Yes 
g. Aspirin	No 	Yes 
h. Plavix	No 	Yes 
i. Warfarin	No 	Yes 

Form Completed By _____ Date _____

VISIT (Months)

--	--

SITE NO.

--	--	--

SUBJECT ID

--	--	--	--	--

ALPHA CODE

--	--	--	--	--

FORM 12 – PHONE CALL FOLLOW-UP FORM

1. Date of phone call (*or medical chart review*)

--	--

--	--

--	--	--	--	--

Month Day Year

2. Subject contacted successfully? No Yes

3. Did the subject die since the last contact? No Yes
If yes, (complete Forms 14 and 15)
a. Date of death

--	--

--	--

--	--	--	--	--

Month Day Year

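### No rule in the supplied text sends index-admission MIs to the masked events committee: Form 06 records two of the Appendix C criteria but does not route them, so referral depends on a site that knows the arm

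*Protocol*

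**What the plan says.** **Knowledge of the arm.** Protocol Appendix D has the site coordinator obtain the allocation by telephone: "Once the required information is entered in the system, the system will return the assignment for the patient". No masking of site staff is described. Masking applies to the Clinical Events Committee, whose documents are edited "to remove subject identifiers and any reference to treatment arm received" (Protocol XV.A).

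**The committee's remit.** For deaths, XV.A provides a coordinator-prepared packet for every case. For MI the wording is narrower: "this committee will evaluate and confirm all reported myocardial infarctions (MI"). Form 20 asks the committee for a yes or no on a numbered MI and ends at no. Form 19, the local-site confirmation, comes before it. Both are scheduled as needed.

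**The definition.** Appendix C states its aim in clarifying the definition: "capture every and all MI events during the conduct of the study while minimizing the volume of site reports that do not meet" it. In the first 48 hours it requires a peak troponin above 10 times the 99th-percentile upper reference limit (URL), plus at least one ECG, angiographic or imaging finding.

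**The forms.** Form 06 (Q2 for day 1, Q12 for day 2) asks about new Q waves or new left bundle branch block and continues: "If yes, obtain Cardiac Biomarkers of choice every 8 hours until downward trend is seen in level and" record the peak value with its reference range. Form 11 at six weeks asks directly about MI and adds "If yes, complete form 15 and 19". Form 12 carries the same instruction.

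**The concern.** MI is one of three components of the primary composite, and the one that depends most on applying a definition. Where sites know the arm, masked adjudication protects that component only if the decision to refer a case is not itself made with knowledge of the arm.

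For the index admission the printed forms leave that decision to the site. Form 06 could show a positive ECG item and a very high peak marker, and no Form 19 need follow. The case would then sit in the database without adjudication. If the threshold for declaring an MI differed between endoscopic and open harvest, the referral rates would differ too, and no planned table would show it. If it were merely high in both arms, events would be lost and power would fall.

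**Working it through.** **1. Routing, form by form (Protocol Appendix E)**

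| Form | Time | MI content | Onward instruction printed |
|---|---|---|---|
| 06, Q2 and Q12 | Days 1 and 2 | No MI item; ECG item, and peak biomarker if ECG positive | None to Form 15 or 19 |
| 07 | Discharge | None | None |
| 11, Q2 | Six weeks | MI since the last contact | Forms 15 and 19 |
| 12, Q4 | Every three months | MI since the last contact | Forms 15 and 19 |
| 15 | As needed | Box for non-fatal MI, completed by the site | None to the committee |
| 19, then 20 | As needed | Site confirmation, then committee yes/no | Form 20 stops if no |

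Forms 11 and 12 look back only to the last contact. The adjudication trigger in Protocol IX.C applies to events reported after discharge. Neither systematically reaches an MI during the index stay.

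**2. What Form 06 can show.** It holds the ECG criterion and the biomarker, a pair that can satisfy Appendix C. There are two limits. IX.C says the form will collect the 99th-percentile URL, but the printed form has only a reference range, so the 10-fold test may not be computable from it. The angiographic and imaging criteria appear on Form 19 and not on Form 06.

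**3. Which MI is analysed.** Protocol XVII.D.2 and SAP 2.2.1 and 7.1 define MACE without saying whether a Form 19 or a Form 20 MI counts.

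**4. Size.** The plan gives no figure for missed MIs. Its nearest figure is the one-year sample size (Protocol XVII.B, SAP 3.6), which reproduces. With rates 0.155 and 0.095, mean 0.125, two-sided 5% and 85% power:

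n = [1.96·√(2·0.125·0.875) + 1.036·√(0.155·0.845 + 0.095·0.905)]² / 0.06² = 545 per group after rounding up, as stated.

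For the illustration:

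- Protocol Table 1 gives one-year non-fatal MI of (60 + 33)/(587 + 778) = 93/1365 = 6.8%, against a composite of (96 + 46)/1365 = 142/1365 = 10.4%.
- Assumptions: no true difference; one-year MACE 12.5% in both arms; 1150/2 = 575 per arm; MI is the qualifying event in 4% to 6.8% of patients; 10% or 20% of those MIs go unreferred in one arm only.
- Shift = unreferred fraction × MI share. SE = √(2·0.125·0.875/575) = 0.0195. Error = P(|Z + shift/SE| > 1.96).

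| Unreferred, one arm | MI share | Shift (points) | Two-sided error |
|---|---|---|---|
| 10% | 4% | 0.40 | 5.5% |
| 10% | 6.8% | 0.68 | 6.4% |
| 20% | 4% | 0.80 | 7.0% |
| 20% | 6.8% | 1.36 | 10.7% |

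If only half of these MIs were perioperative, a 20% shortfall confined to them gives the shifts in the 10% rows (0.20 × 3.4% = 0.68; 0.20 × 2% = 0.40), so 5.5% to 6.4%. The documents do not give the perioperative share.

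On power, an assumed loss of 0.5 or 1 point in the endoscopic arm alone lowers one-year power at 545 per group from 85.1% to 79.2% or 72.0%. If 10% of all MACE were missed equally in both arms, it would be 80.6%.

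**The case against.** **Other sources of events exist.** A reader might infer that, throughout the trial, only site-declared MIs can reach the committee. The documents do not support that. After discharge, a subject's report leads to records for adjudication (IX.C), the VA record is checked when a subject cannot be reached (X.E), outside-hospital material is reviewed centrally (XI.B), and VA databases are searched for potential drop-outs (XVII.G, SAP 5.3). In hospital, serious adverse events are collected, and failure to report one is a noncompliance code. This stands, and it confines the point to the index admission. None of these sources is said to screen Form 06, and no route from Form 15 to the committee is printed.

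**The committee's powers.** It is tempting to say the committee can remove MIs but never add one. With no rule on which determination is analysed, removal is an inference. Never adding one rests on silence, not on a prohibition.

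**Appendix C.** It could be read as asking sites to hold reports back. It does not: the sentence gives the purpose of clarifying a definition. The passage about findings that "do not provide a complete diagnostic profile to the satisfaction of the surgeon investigator" concerns a further echocardiogram and is not a reporting filter.

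**Unseen material.** Form 13 (the MACE event form) and the operations manual were not available, and either could hold a routing instruction. This stands as a limit on the claim.

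**The arithmetic.** It applies a gap on days 1 and 2 to all one-year MIs. It tests a one-year proportion, whereas the primary analysis is time-to-event. It also ignores that a patient with a missed MI who later dies or is revascularized still counts as MACE. All three objections stand.

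**Conclusion.** The point holds for the index admission. In the supplied text, nothing carries a perioperative MI to the masked committee except a declaration by a site that knows the arm, although Form 06 already records the ECG and biomarker findings. The missing rule on whether Form 19 or Form 20 MIs enter the primary endpoint is a second, related gap.

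The size is unknown. A reader might take the 5.5% to 11% error range as an estimate of the bias. It is an upper illustration that covers all one-year MIs and rests on assumed under-referral of 10% or 20% in one arm; the documents give neither a referral rate nor a perioperative share. Against the planned 6-point difference, the assumed shifts of 0.4 to 1.4 points are modest. No sample-size figure changes. The case for acting is that the change is cheap and takes an arm-aware judgement out of a primary-endpoint component. The conclusion assumes that Form 13 and the operations manual contain no such rule.

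**What to change.** 1. **Form 06, Q2 and Q12:** add an instruction to complete Form 19 if the answer is Yes. Trigger on the positive ECG item, because the printed form lacks the 99th-percentile URL. If a biomarker trigger is preferred, add that field first.
2. **Protocol XV.A:** have the national nurse coordinator send the committee an arm-scrubbed packet for every positive Q2 or Q12 and every Form 15 marked non-fatal MI, whether or not the site declares an MI. The Form 15 trigger covers an index-admission MI identified by angiography or imaging, provided the site reports it as a serious adverse event.
3. **SAP 2.2.1 and 7.1:** state that committee-confirmed (Form 20) MIs define the MI component of the primary endpoint, and report by arm the numbers triggered, declared and confirmed.

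Packets for every PCI, CABG or death are not needed for this purpose, since those patients already count as MACE. The purpose statement in Appendix C can stay as it is. If Form 13 or the operations manual already has a routing rule, citing it in XV.A would replace items 1 and 2 to the extent that it covers them.

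The cost is a line at two places on one form, a short addition to the protocol and the SAP, and some additional packets for the existing coordinator and a three-member committee that meets twice a year. Patient care does not change.
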